- Expression of genes implicated in GIST pathogenesis and signaling, including KIT, ETV1, FGFR1, -2, -3, and -4; DUSP6, SPRY2, and SPRY4.
- Cell proliferation (Ki-67) and apoptosis (cleaved caspase-3) by IHC

MEMORIAL SLOAN-KETTERING CANCER CENTER IRB PROTOCOL

IRB#: 14-140 A (7)

- MAP kinase pathway and other pathways downstream of KIT signaling using standard antibodies (phospho-ERK, phospho-KIT, phospho-MEK, phospho-AKT) by IHC
- *KIT/PDGFR* mutational status in matched tumor biopsy specimens collected prior to therapy, after combination therapy and upon disease progression. *FGFR* and *FGF2* expression on tumor samples by IHC and *FGF2* ligand levels in collected serum by ELISA.
- Protein expression of *FGF2*, *sVEGFR1*, *sVEGFR2*, *VEGF-A*, *-C*, *-D*, *cKIT*, *PLGF*, and *Tie2* in tumor tissues utilizing commercially available immunoassay kits

We will also monitor the effect of BGJ398 on imatinib serum levels by measuring the steady-state imatinib serum trough levels at the end of the 2-week lead in imatinib alone phase and after the combination of BGJ398 and imatinib therapy at week 3 and week 5 (C1W3 and C2W1).

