9.0 TREATMENT/INTERVENTION PLAN

Treatment will be administered on an outpatient basis. Reported adverse events and potential risks are described in Section 11. Appropriate dose modifications of imatinib and BGJ398 are described in section 9.2. No investigational or commercial agents or therapies other than those described below may be administered with the intent to treat the patient's malignancy.

MEMORIAL SLOAN-KETTERING CANCER CENTER IRB PROTOCOL

IRB#: 14-140 A (7)

Imatinib will be self administered orally by the patient on a daily basis throughout the treatment cycle. The standard treatment dose is 400 mg PO QD. 400 mg capsule will be used unless otherwise specified by the treating physician. BGJ398 will be taken at the RP2D and treatment schedule chosen from the Phase Ib portion of the trial. The RP2D selected may be lower than the MTD based on PK data and clinical tolerance beyond Cycle 1. BGJ398 is taken daily for a duration determined by the treatment schedule appropriate for the given dose level. In the event of dose delays of BGJ398, Day 1 of the following cycle will be defined as the day that BGJ398 is restarted. A pill diary for both medications will be provided and recorded (Appendix B). This will be used to assure compliance with the regimen.

On the Phase Ib portion, the timing of pharmacokinetic sample collections will be dependent on the treatment schedule onto which that patient is enrolled. For treatment schedule A pharmacokinetic samples will be drawn on Cycle 1, Day 1 at the following timepoints: 0, 1, 2, 4, 6, 8, and 24 hrs; and Cycle 1, Day 21 at the following timepoints: 0, 1, 2, 4, 6, and 8 hours. For treatment schedule B pharmacokinetic samples will be drawn on Cycle 1, Day 1 at the following timepoints: 0, 1, 2, 4, 6, 8, and 24 hrs; Cycle 1, Day 7 at the following timepoints: : 0, 1, 2, 4, 6, and 8 hours, Cycle 1, Day 15 at timepoint 0hr and Cycle 1, Day 21 at timepoint 0hr.

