
Key for Table 10:
 
Schedule of Phase 2
 
Evaluations
	
X: Imatinib: Dose as assigned; PO once daily
 
Y: BGJ398: Dose as assigned; PO once daily the treatment schedule will be determined by the phase 1b portion of the study
 
a: Comp- Albumin, alkaline phosphatase, total bilirubin, bicarbonate, BUN, calcium, chloride, creatinine, glucose, potassium, total protein, SGOT [AST], SGPT [ALT], sodium. In addition, LDH, phosphorus, magnesium, creatine kinase (CK), amylase, lipase.
 
b: Blood pregnancy test (women of childbearing potential) once at baseline; blood or urine pregnancy test at the discretion of the investigator while on study.
 
c: Off-study evaluation performed 4 weeks after removal from study.
 
d: Day 1 of every cycle while on study. At the investigator's discretion, patients can return for RN/MD visits and get evaluated every 8 or 12 weeks after cycle 4. Laboratory assessments and EKG assessments between MD/RN visits can be performed locally with results sent to the study site
 
e: TTE or MUGA will be performed once at week 16 as well as any time felt to be necessary by the investigator. Modalities should remain consistent whenever feasible.
 
f: Scans should be performed every 8 weeks x 4 starting after 2 cycles (e.g. C3D1, C5D1, C7D1, C9D1), then every 12 weeks (C12D1, C15D1, etc). Radiologic documentation must be provided for patients removed from study for progressive disease within 28 days of clinical assessment of progression if no scan was performed within 28 days of the time of that assessment.
 
g: FDG PET scan will be performed at baseline (pre-treatment) and during week 3 of combination therapy (C1D21).
 
h: Tumor biopsy will be performed pre-treatment, after week 1 (C1D8) of therapy, and at disease progression for patients who have consented for research biopsies including the first twenty mandatory patients and any subsequent voluntary patients. A +/- 4 day window will be provided for the biopsies to account for scheduling.
 
i: Four research blood 4-8mL vials will be obtained at baseline (week -2), two weeks after the single agent imatinib lead in (C1D1 of combination therapy), week 3 (C1D15), week 5 (C2D1). At least one tube at those timepoints will be used for imatinib trough levels, and two tubes will be used for correlative analyses. Imatinib levels will be prioritized.
 
j: Two research blood 4-8mL vials for correlative analyses will be obtained at the time of progression.
 
k: At eye exams the follow tests should be completed : - slit lamp exam - dilated funduscopic exam with photos - optical coherence tomography testing A follow-up eye exam will occur at week 4 (C1W4) and if the patient develops new or worsening ocular symptoms.
 
l: Study personnel will attempt to contact all evaluable patients every 3 months (± 2 weeks) via telephone, email, etc to assess survival status for up to 3 years.
 
m. CBC and Blood Chemistry performed on Day 1 of each cycle must be resulted prior to treatment
 
All assessments are to be done +/-3 days of the scheduled timepoints unless otherwise noted. Radiologic assessments (CT, PET, TTE) are to be done +/-7 days from the scheduled appointment.

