Research blood will be drawn on the Phase Ib portion at the time points noted in Tables 10.A and 10.B for BJJ398 and imatinib plasma levels. Research blood will be obtained on the Phase II portion at baseline, 2 weeks after single agent imatinib lead in (+/-3 days) prior to Cycle 1 Day 1, and at C1D15 and C2D1 after the combination therapy started from all patients. All blood samples should be obtained prior to the daily dose of imatinib +/- BJJ398; i.e. a trough level. Research blood will be used to evaluate the steady-state imatinib trough level.

10.2.4 Collection of Specimen(s):

Tumor samples will be collected pre-treatment from the first 20 patients enrolled on the Phase II portion of the trial who have accessible tumor for biopsy and will start imatinib de novo for this trial. Also, tissue will be collected from any subsequent patients who require standard of care biopsies prior to systemic treatment, or those patients who volunteer for research biopsies if funding is available.

MEMORIAL SLOAN-KETTERING CANCER CENTER
IRB PROTOCOL

IRB#: 14-140 A (7)

10.2.4 Handling of Specimens(s):

For each sample indicate the unique patient study identification number, histology diagnosis, and the date of the specimen.

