Response rate (RECIST 1.1) will be determined as the proportion of patients evaluable for efficacy (defined as patients who receive at least one dose of the combination regimen) who have complete response or partial response defined by the RECIST 1.1 with a one-sided 90% confidence interval (CI) provided. Patients missing post baseline assessment of response will be considered non-responders for the primary endpoint at that time point.

The steady state serum imatinib trough levels will be obtained and evaluated in the two-week imatinib lead in phase (two samples/patient) and in the combination therapy phase (2 samples/patient) from all patients in the Phase II portion of the trial. We will evaluate the effects of BGJ398 on imatinib steady state trough levels by comparing the values at these two time points (before and after lead in period). We will compare the ranges we obtain with the ranges reported by Demetri et al JCO 2009 and assess whether the effects are considered subtherapeutic, therapeutic, or

MEMORIAL SLOAN-KETTERING CANCER CENTER
IRB PROTOCOL

IRB#: 14-140 A (7)

supra-therapeutic. This analysis may inform future trials with this combination and will not change the dose that will be given in the combination regimen.

The secondary endpoints of the phase 2 portion include:

- (1) RR by CHOI criteria. It will be determined as the proportion of patients evaluable for efficacy who have complete response or partial response defined by the CHOI criteria with a two-sided 95% CI provided.
- (2) RR by EORTC criteria. It will be determined as the proportion of patients evaluable for efficacy who have complete response or partial response defined by the EORTC criteria with a two-sided 95% CI provided.
- (3) Progression free survival and Overall Survival. PFS and OS will be calculated using a Kaplan-Meier estimate among all patients enrolled. They are defined from the start of imatinib treatment, i.e. the lead in period is included in this endpoint. Patients on the Phase II portion who stop study prior to receiving a dose of BGJ398 for reasons unrelated to progression (e.g. intolerance to imatinib) will be censored at the time of withdrawal. Patients who have not had the event of interest by the end of the study will be censored at the time of last follow-up.
- (4) Resectability rate. It will be calculated by the proportion of Phase II patients who have completed 1 cycle of treatment who have resection of their disease with a two-sided 95% CI provided.

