MSKCC-Assigned Participant ID:	
Contents – Sample Information	
Date of Collection: (MM DD YYYY)	Phase I Study Time Point:
	 Cycle 1 Day 2 (24 hours post-first dose / Pre-dose on Day 2)
	 Cycle 1 Day 7 (Pre-dose)
	 Cycle 1 Day 21 (Pre-dose)

Shipment Information		Sender's Contact Information	
Shipping Date		Name	
Shipping Method		Email	
Tracking Number		Telephone	

For MSKCC Use ONLY: Date received at MSKCC: __ / __ / ____ (MM DD YYYY)

MEMORIAL SLOAN-KETTERING CANCER CENTER
IRB PROTOCOL

IRB#: 14-140 A (7)

Phase II: Research Blood Collection

Pharmacokinetic Samples for Imatinib and FGF Serum Levels

Supplies for each sample collection and storage:

- (2-4) 4-8 mL K3-EDTA tubes – provided by site
 - (2) 1.8 mL NUNC 2D coded tubes from Thermo – provided by site
- Reference for tubes: 374502NOV (1D/2D coded tubes) or 374502 (480 tubes/10 bags)

Phase II Collection procedures for Imatinib PKs and FGF Serum Research bloods:

1. Use (4) 4-8mL K3-EDTA tubes for collection at timepoints: Week -2, C1D1, C1D15, C2D1. Use (2) 4-8mL K3-EDTA tubes at the time of progression.
2. All blood samples will be taken by either direct venipuncture or an indwelling catheter inserted in a forearm vein.
3. At specified timepoints, collect a 2mL blood sample in tubes with the specific coagulant K3-EDTA
4. Immediately after blood draw, invert gently several times to ensure mixing of contents. Avoid prolonged blood sample contact with the rubber stopper.
5. Place the tube upright surrounded by ice or cryoblock until centrifugation.
6. Within 30 minutes, centrifuge the sample between 3-5°C for 10 minutes at approximately 2000g.
7. Immediately after centrifugation, 2 aliquots of about 0.5 mL of the collected plasma should be transferred into labeled 1.8 mL NUNC 2D coded tubes from Thermo. At least 0.5 mL of plasma in the first tube and the remaining plasma into the second tube.
8. Immediately freeze the tubes over dry ice (solid carbon dioxide) then keep frozen at $\leq -15^{\circ}\text{C}$.

Labeling and Shipping Instructions:

1. Label samples with MSKCC ID, date of collection, and study time point.
2. Participating sites will ship specimen to MSK. All shipments should be directed to the address listed on the tissue sample shipment form. Samples should be shipped frozen with dry ice by courier so that the package can be tracked appropriately (specifically, Federal Express or UPS).

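### Section 14 words the test of BGJ398's effect on imatinib troughs as before versus after the lead-in, when no BGJ398 has been given, and the combination draw days are not tied to the BGJ398 schedule

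*Combined protocol and SAP*

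**What the plan says.** Section 14.0, phase 2 portion, says imatinib troughs will be obtained "in the two-week imatinib lead in phase (two samples/patient) and in the combination therapy phase (2 samples/patient"). The next sentence says the effect of BGJ398 will be evaluated "by comparing the values at these two time points (before and after lead in period"). The section adds that the analysis may inform future trials and will not alter the dose given.

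Other places describe the same analysis differently:

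- Section 2.0 sets the end of the lead-in against levels "after the combination of BGJ398 and imatinib therapy at week 3 and week 5 (C1W3 and C2W1").
- Section 10.2.5, item 1g, gives one sample per patient in each phase and compares the two phases.
- Section 9.0 has BGJ398 added only after the end-of-lead-in draw. It places the repeat draw about 3 to 5 weeks after the combination starts, to obtain a trough with BGJ398 present.

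The operative draw days are in Table 11, note i (Section 10.1.2), and the lab manual (Appendix I): "Use (4) 4-8mL K3-EDTA tubes for collection at timepoints: Week -2, C1D1, C1D15, C2D1". Note i adds: "At least one tube at those timepoints will be used for imatinib trough levels". Section 10.2.3 makes every draw pre-dose: "All blood samples should be obtained prior to the daily dose of imatinib +/- BJJ398". The general window is "All assessments are to be done +/-3 days of the scheduled timepoints unless otherwise noted".

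Section 5.2.3 allows two BGJ398 schedules in a 28-day cycle: A, 21 days on and 7 off; B, 7 days on and 21 off. Table 11 leaves the phase II choice to phase Ib. If BGJ398 is delayed, Section 9.0 states: "Day 1 of the following cycle will be defined as the day that BGJ398 is restarted".

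**The concern.** Section 14.0 is where an analyst looks for the comparison to run. Taken literally, its parenthesis selects two samples with no BGJ398 exposure. The difference between them would show imatinib building up from nothing and could say nothing about BGJ398.

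Correcting the words leaves a second question: which combination draw shows imatinib with BGJ398 present? The draw days do not depend on the schedule, so a sample labelled as combination may have been taken during the BGJ398 off-period.

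The stake is the purpose given in Section 10.2.5, item 4: to check that BGJ398 does not alter the level of the standard-of-care drug. Section 3.3.3.1 names CYP3A4 as the main enzyme for imatinib. Section 3.2.2.1 reports that BGJ398 inhibits it in vitro. Section 9.4.2 says such interactions have not been confirmed in patients.

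**Working it through.** The plan states no figure to reproduce here. The check is a count of days.

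**Inputs.** C1D1 is Day 1 and C2D1 is Day 29 (28-day cycle, no delay). Cycle 1 BGJ398 days are 1-21 under A and 1-7 under B (Section 5.2.3). All draws are pre-dose (Section 10.2.3). The window is plus or minus 3 days (Table 11 key). The imatinib half-life is 18 h, range 10 to 23 h (Section 3.3.3.1).

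**Formulas.** Doses before a pre-dose draw = number of dosing days strictly earlier than the draw day. Days since last dose = draw day minus last dosing day.

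**The literal comparison.** Week -2 and C1D1 each follow 0 BGJ398 doses under both schedules. Week -2 also follows 0 study imatinib doses, and any adjuvant imatinib must have ended at least 90 days before registration (Section 6.2). C1D1 is a sound reference: 14 days x 24 h = 336 h, which is 336/18 = 18.7 half-lives, or 336/23 = 14.6 at the slow end. The fraction of steady state reached is 1 - 0.5^14.6, above 99.99%.

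**Sample counts.**

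| Source | Lead-in | Combination |
|---|---|---|
| Section 14.0 | 2 | 2 |
| Section 10.2.5, item 1g | 1 | 1 |
| Calendar and lab manual, draws | 2 (week -2, C1D1) | 2 (C1D15, C2D1) |
| Calendar and lab manual, steady-state lead-in troughs | 1 (C1D1) | not applicable |

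Section 14.0 agrees with the calendar as a count of draws. It does not agree as a count of steady-state lead-in troughs.

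**Combination draws against the schedules.**

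| Draw | Schedule A | Schedule B |
|---|---|---|
| C1D15 (Day 15) | 14 prior doses, last one the day before: on BGJ398 | 15 - 7 = 8 days since last dose |
| C1D15 over the window (Days 12-18) | 11 to 17 prior doses, still on | 12 - 7 = 5 to 18 - 7 = 11 days |
| C2D1 (Day 29), before the first cycle 2 dose | 29 - 21 = 8 days | 29 - 7 = 22 days |
| C2D1 up to 3 days early (from Day 26) | 26 - 21 = 5 to 8 days | 26 - 7 = 19 to 22 days |

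On the planned days, Schedule A has one on-BGJ398 draw and Schedule B has none. Because Day 1 of a delayed cycle is the day BGJ398 restarts, a delay lengthens the C2D1 gap; it does not turn C2D1 into an on-drug draw.

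**Section 9.0 timing.** Three to five weeks after Day 1 is Days 22 to 36. Read literally, that leaves out C1D15 (14 days after the start), the draw that is on BGJ398 under Schedule A.

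**What the gaps mean.** If inhibition ended with the last BGJ398 dose, imatinib would have nearly re-equilibrated after 8 days: 0.5^(192/23) = 0.3% of the shift would remain at the slowest half-life. But the documents give no BGJ398 elimination half-life and no CYP3A4 recovery time, and Section 3.2.2.1 also reports time-dependent inhibition. The residual effect at 5, 8 or 22 days cannot be calculated.

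**The case against.** The best reply is that the intent is already on record. The sentence before the parenthesis names the lead-in and combination phases, and Section 10.2.5 compares those phases outright. Section 2.0 agrees. The combination samples are collected in any case, and the analysis is descriptive, outside the numbered secondary endpoints and without effect on dose. Two plus two does match the four calendar draws. Schedule B is a contingency at the principal investigator's discretion. All of this stands, and it keeps the point minor.

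It does not remove the point. The analysis section still states a comparison that contradicts the rest of the plan, and no passage gives a phase II draw on BGJ398 if Schedule B is chosen. Phase Ib does adapt its imatinib draws by adding C1D7 under Schedule B (Table 9, note i); phase II does not.

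A reader might infer more than the documents support:

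- That the trial cannot detect an interaction. Under Schedule A, C1D1 versus C1D15 is a usable within-patient contrast, and C1D15 versus C2D1 is another on/off pair.
- That the plan pools C1D15 with C2D1. No passage proposes it.
- That an off-period draw shows no interaction, or understates one by a known amount. Off describes dosing only; the size cannot be derived.
- That 8 and 22 days are minimum gaps at C2D1. Early draws within the window shorten them to 5 and 19.

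**Conclusion.** The point holds as a minor error of wording and alignment. As written, the Section 14.0 comparison contains no BGJ398 exposure; the comparison evidently intended is end of lead-in against combination. Sample counts conflict between Sections 14.0 and 10.2.5, and neither states the calendar's one steady-state lead-in trough plus two combination draws. Under Schedule A one of the two combination draws is on BGJ398; under Schedule B neither is. The primary endpoint, the decision rule and dosing are unaffected.

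The day counts assume cycle 1 dosing without interruption, 28-day cycles, pre-dose draws, and a week -2 sample taken before the first study imatinib dose. The wording and sample-count points do not depend on any assumed effect size or on which schedule is chosen.

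**What to change.** In Section 14.0, replace the parenthesis with a within-patient comparison of the C1D1 trough (end of lead-in, before BGJ398) with an on-BGJ398 trough, and state that the week -2 sample is not used.

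- **Schedule A:** name C1D15 as the on-BGJ398 trough. Report C2D1 separately as drawn in the BGJ398 off-period, and require that draw before the first cycle 2 dose.
- **If Schedule B is selected:** move one combination imatinib tube to an on-BGJ398 pre-dose day. C1D7 matches phase Ib. C1D8, 24 h after the Day 7 dose, fits the existing week 2 visit. Use a window that does not run late, such as the -2/0 days that phase Ib sets for C1D7.
- **Reconcile:** give one sample count (one lead-in trough, two combination draws) and one set of draw days in Sections 2.0, 9.0, 10.1.2 (Table 11, note i), 10.2.3, 10.2.5 (items 1g and 4) and 14.0, and in the lab manual.

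The cost is text edits. Under Schedule A no draw changes day; only the late side of the C2D1 window closes. Under Schedule B one tube changes day. C1D7 may need its own visit, while week 2 already has blood draws. The small downside is that imatinib and FGF2 would not be measured on the same day at that time point. The wording should be settled before phase II samples are analysed, and the Schedule B draw before phase II opens.

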12.1.14 Progression-Free Survival (PFS)

PFS is defined as the period from start of study treatment until recurrent or progressive of disease (POD) is objectively documented (taking as reference for progressive disease the smallest measurement recorded on study), death, or date of last contact. For the Phase II portion, start of treatment is defined as the start of the imatinib lead-in period.

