12.1.15 Overall Survival (OS)

OS is defined as the observed length of life from study entry to death or the date of last contact.

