Duration of Follow Up: Patients will be followed for toxicities 4 weeks after last dose or until death, whichever occurs first. Patients removed from study for unacceptable adverse events will be followed until resolution or stabilization of the adverse event. For Phase II, study personnel will attempt to collect survival status for all patients after the end-of-study visit every 3 months via telephone, email, or other method for up to 3 years.

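### Overall survival is censored at withdrawal for Phase II patients who stop before BGJ398 without progression, so any death found later in the planned survival follow-up would not be counted

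*Combined protocol and SAP*

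**What the plan says.** Section 14.0, Phase II secondary endpoint (3), treats PFS and OS together. On population: "PFS and OS will be calculated using a Kaplan-Meier estimate among all patients enrolled". On time origin: "They are defined from the start of imatinib treatment, i.e. the lead in period is included in this endpoint". It then sets a special rule: "Patients on the Phase II portion who stop study prior to receiving a dose of BGJ398 for reasons unrelated to progression", with imatinib intolerance as the example, "will be censored at the time of withdrawal". Everyone else without the event is censored at last follow-up. Nothing limits the special rule to PFS.

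Four other places bear on it:

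- Section 12.1.15: "OS is defined as the observed length of life from study entry to death or the date of last contact". It has no censoring at withdrawal.
- Section 13 (Duration of Follow Up), for Phase II: "study personnel will attempt to collect survival status for all patients after the end-of-study visit every 3 months", for up to 3 years. Section 4.2 says the same.
- Section 10.1.2, Table 11, note l: "Study personnel will attempt to contact all evaluable patients every 3 months".
- Sections 12.1.1 and 13 make patients who leave before BGJ398 for reasons other than progression replaceable. Section 12.1.1 says this is for evaluating the primary and secondary endpoints.

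**The concern.** For PFS, censoring at withdrawal has a rationale: response imaging is scheduled for the treatment period, so progression may go unobserved afterwards. That reason does not carry over to OS. Death can be ascertained after treatment stops, and the protocol plans to ask. Under the shared rule, a death learned of at a 3-monthly contact falls after the patient's censoring date and does not count.

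Kaplan-Meier estimation needs the censored patients to have the same later survival as those who remain. The protocol's own example of an early leaver is someone who cannot tolerate imatinib, the standard first-line drug, so the assumption is open to doubt. If leavers do worse, the OS curve described as covering all enrolled patients is too high, in the regimen's favour.

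Two inconsistencies add to this. The contact population differs between Sections 4.2 and 13 and the Phase II calendar, and follow-up that a site does not collect may not be recoverable. The OS clock starts at study entry in one section and at the start of imatinib in another.

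**Working it through.** **No OS figure to reproduce.** The documents state no OS target, event count or power. The nearest stated design figure, the response rule, does reproduce: success at 25 or more of 44 gives an exact one-sided type I error of 0.0775 at a true rate of 45% (stated 0.08), and power 0.9011 at 65%, so a type II error of 0.0989 (stated 0.1). That rule uses patients who received at least one dose of the combination, so OS censoring does not touch it.

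**Three patients under the text as written.**

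1. *Receives BGJ398, stops later, dies in year 2.* An event under Sections 12.1.15 and 14.
2. *Stops in the lead-in for intolerance, dies in year 2, death found by the planned contact.* An event under Section 12.1.15; censored at about week 2 under Section 14. The two sections conflict, and the death is lost if Section 14 governs.
3. *Dies during the lead-in while still on study.* An event. Sections 12.1.14 ("death, or date of last contact") and 12.1.15 both name death, and the special rule concerns stopping and withdrawal.

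The loss is therefore confined to deaths after withdrawal, in patients who left before BGJ398 without progression. The lead-in is 2 weeks.

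**Size.** The inputs below are assumptions, apart from the 44.

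- 44 patients reach BGJ398 (the Section 14 sample size). A further k leave early and are replaced, so 44 + k are enrolled; k = 1 to 6.
- S1, 3-year OS in those who reach BGJ398: 0.70 to 0.80.
- S2, 3-year OS in early leavers: 0.30 up to S1.
- Survival status at 3 years is known for everyone.

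Leavers censored at about week 2 contribute almost nothing, so the censored estimate is about S1. With full follow-up it is (44·S1 + k·S2)/(44 + k). The difference is k·(S1 − S2)/(44 + k).

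Shift in points at S2 = 0.30:

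| k | Enrolled | S1 = 0.70 | S1 = 0.80 |
|---|---|---|---|
| 1 | 45 | 0.9 | 1.1 |
| 2 | 46 | 1.7 | 2.2 |
| 4 | 48 | 3.3 | 4.2 |
| 6 | 50 | 4.8 | 6.0 |

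Examples: k = 2, S1 = 0.80: 2 × 0.50/46 = 0.022. k = 6, S1 = 0.80: 6 × 0.50/50 = 0.060, that is 0.800 against 0.740. At S2 = S1 the shift is 0 for every k. Expected deaths left out, k·(1 − S2), run from 1 × 0.20 = 0.2 to 6 × 0.70 = 4.2.

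For scale, the binomial standard error with 44 patients is √(0.80 × 0.20/44) = 6.0 points at 80% and √(0.70 × 0.30/44) = 6.9 points at 70%.

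**Contact population.** Note l does not say which sense of *evaluable* it means. Section 12.1.1 gives two. For efficacy, a patient needs a dose of imatinib plus BGJ398, so early leavers are out. For toxicity, Phase II patients count from their first imatinib dose, so they are in.

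**Time origin.** *Study entry* is not defined. Section 10.1.2 allows consent 30 days before study start. If entry means consent, the two OS definitions can differ by up to about 30 days per patient; if it means the first imatinib dose, they coincide.

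**The case against.** The strongest reply is that this is small and partly deliberate. The rule covers exits in a nominal 2-week window and affects a secondary endpoint with no test or threshold. With two leavers, the shift is well inside sampling error. Because these patients are replaceable for secondary as well as primary endpoints, focusing on patients who reached BGJ398 looks like a design choice. All of this stands as a limit on importance. It does not reconcile the text: Section 14 still names all enrolled patients as the OS population, and Section 12.1.15 still runs OS to death or last contact.

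It is also fair to say that survival status is only to be attempted. If note l governs in its efficacy sense, the deaths may never be sought, so little known information would be discarded. That is a reason to settle note l.

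A reader might infer more than the documents support:

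- *That note l excludes early leavers.* It is ambiguous, as shown above.
- *That deaths in the lead-in would be censored.* A death on study is not a withdrawal, and both endpoint definitions count it.
- *That OS is shown to be biased upward.* The documents hold no survival data on early leavers, who may leave for any non-progression reason. Zero bias is possible, and the direction depends on an assumption.
- *That OS becomes an estimate only in patients who reached BGJ398.* Leavers still count until withdrawal, and those who leave for progression fall outside the rule.
- *That PFS should count every later death as an event.* For patients no longer scanned, that would need its own rule for the unassessed interval. The point here concerns OS.

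**Conclusion.** The point holds for OS. Section 14, read literally, censors at withdrawal a group whose survival the protocol plans to follow, against its own stated population and its definition in Section 12.1.15. Deaths found after such a withdrawal would not be counted. Whether this biases OS depends on whether leavers' survival differs from the rest; worse survival would bias it upward. Under the assumptions shown, the 3-year estimate moves by 0 to 6 points, and by 0 to 2.2 points with two leavers. The contact-population mismatch matters because it decides whether these deaths are looked for. The time-origin mismatch is minor. Neither the go/no-go response rule nor its error rates are affected. The point merits correction because the change is cheap, but it does not threaten the trial's main conclusion.

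**What to change.** 1. In Section 14, secondary endpoint (3), separate the OS rule from the PFS rule. For OS, the event is death from any cause, and a patient without it is censored only at the last date known alive, whatever the reason for stopping treatment. A patient who refuses all further contact is then censored close to withdrawal anyway.
2. State that the OS set is every enrolled Phase II patient, including those replaced for the response endpoint.
3. Use the start of imatinib as the OS origin in both Section 12.1.15 and Section 14.
4. Change note l of Table 11 from evaluable patients to all Phase II patients, to match Sections 4.2 and 13.

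The cost is an amendment to the wording plus, at most, a few survival contacts that Sections 4.2 and 13 already promise. No sample size, visit or primary analysis changes.
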